Reported ocular symptoms, problems or complaints (0 = No, 1 = Yes) at any visit will be analyzed using a GEE model for clustered binary outcome to assess the difference between the Test and Control groups. The regression model will include terms for lens group, time (1-, 2-, 4-, 8- and 12-week) and the lens group by time interaction. Appropriate working correlation matrix will be selected to take on consideration the correlation between measurements within each subject using Quasi-likelihood Information Criterion (QIC). Working correlation structures to be considered will include exchangeable, autoregressive AR(1) and unstructured (UN). Odds ratio of outcome 1 between the Test and the Control groups will be calculated with a 95% confidence interval.

If the interaction lens by time is significant at the 0.15 significance level, the difference between the Test and Control will be assessed for each follow-up visit.

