1.4. Statistical Hypotheses for Study Objectives

This is a feasibility study and all the following hypotheses are exploratory in nature. Further analysis may be considered at the discretion of the Study Responsible Clinician.

1.4.1. Primary Hypotheses:

Efficacy

- The Test lens [REDACTED] will be significantly lower than the Control lens (ACUVUE® OASYS®), with respect to Eyestrain caused by glare score. The assessments will be made at the 2-, 4-, 8- and 12-week follow-up visits.
- The Test lens [REDACTED] will be statistically no different than the Control lens (ACUVUE® OASYS®) with respect to distance monocular LogMAR visual acuity. The assessments will be made at the 2-, 4-, 8- and 12-week follow-up visits.

Safety

- The Test lens [REDACTED] will be statistically no different than the Control lens (ACUVUE® OASYS®) with respect to percentage of eyes with grade 3 or higher slit lamp findings (Biomicroscopy). The assessments will be made at each follow-up visit.

1.4.2. Secondary Hypotheses:

Efficacy

- The Test lens [REDACTED] will be statistically no different than the Control lens (ACUVUE® OASYS®) with respect to average wearing time. The assessments will be made at the 2-, 4-, 8- and 12-week follow-up visits.

Safety

- The Test lens [REDACTED] will be statistically no different than the Control lens (ACUVUE® OASYS®) with respect to the percentage of reported symptoms, problems or complaints (yes/no). The assessments will be made at each follow-up visit.

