6. SAFETY

6.1. Analysis Specifications

6.1.1. Level of Significance

All planned analysis for this study will be conducted with a two-sided type I error rate of 5% for primary and secondary hypotheses. Adjustment for multiple comparisons across time will be performed using Bonferroni's method. Both adjusted and unadjusted results will be reported.

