6.2. Safety Endpoint(s)

6.2.1. Definition

The primary safety endpoint is the frequency per eye of any corneal infiltrate or any grade 3 or higher SLF including conjunctival injection, corneal edema, corneal neovascularization, corneal staining, tarsal abnormalities, or any other complications. SLFs will be evaluated using the FDA grading scale ranging from 0 to 4, with grade 0 represents the absence of findings and 1 to 4 representing successively worse findings (i.e. Grade 1 = trace, Grade 2 = Mild, Grade 3 = moderate and Grade 4 = severe).

The safety endpoint will be evaluated at 1-, 2-, 4-, 8- and 12-week follow-up visits and during unscheduled visits. Events occurring during an unscheduled visit will be counted in the subsequent scheduled visit. For example, if a SLF grade 3 or higher occurs between Visit 1 and Visit 2, it will be counted in Visit 2. If there are multiple events at a given time point for one eye, it will be counted only once.

The secondary safety endpoint is the frequency per eye of any reported ocular symptoms, problems, or complaints.

The safety endpoints will be evaluated at 1-, 2-, 4-, 8- and 12-week follow-up visits and during unscheduled visits. Events occurring during an unscheduled visit will be counted in the subsequent visit. For example, if an ocular symptom, problem, or complaint is reported between Visit 1 and Visit 2, it will be counted in Visit 2. If there are multiple events at a given time point for one eye, it will be counted only once.

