Reported ocular symptoms, problems or complaints (0 = No, 1 = Yes) at any visit will be analyzed using a GEE model for clustered binary outcome to assess the difference between the Test and Control groups. The regression model will include terms for lens group, time (1-, 2-, 4-, 8- and 12-week) and the lens group by time interaction. Appropriate working correlation matrix will be selected to take on consideration the correlation between measurements within each subject using Quasi-likelihood Information Criterion (QIC). Working correlation structures to be considered will include exchangeable, autoregressive AR(1) and unstructured (UN).

If the interaction lens by time is significant at the 15% significance level, the difference between the Test and Control will be assessed for each follow-up visit.

For unadjusted estimates the odds ratio of outcome 1 between the Test and the Control groups will be calculated with a 95% confidence interval to test for the difference between the Test and Control groups. For adjusted estimates the odds ratio of outcome 1 between the Test and the Control groups will be calculated with a simultaneous 99% confidence interval to test for the difference between the Test and Control groups.

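### Ocular symptoms are formally compared at each visit only if a lens-by-time interaction passes 15%, which conflicts with a hypothesis and a multiplicity rule that both call for five visits

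*SAP*

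**What the plan says.** SAP 1.4.2 states the secondary safety hypothesis as no statistical difference between lenses "with respect to the percentage of reported symptoms, problems or complaints (yes/no). The assessments will be made at each follow-up visit". Protocol 4.1.4 says the same.

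SAP 6.2.1 defines the endpoint as the "frequency per eye of any reported ocular symptoms, problems, or complaints" and sets the schedule: "The safety endpoints will be evaluated at 1-, 2-, 4-, 8- and 12-week follow-up visits".

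SAP 6.1.1 plans a "two-sided type I error rate of 5% for primary and secondary hypotheses". It adds a Bonferroni adjustment across time and asks for adjusted and unadjusted results, without any condition.

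SAP 6.2.2 fits a GEE model with lens group, time and their interaction. Then comes the condition, "If the interaction lens by time is significant at the 15% significance level", and only then "the difference between the Test and Control will be assessed for each follow-up visit". Protocol 9.1 has the same rule: "If the interaction lens by time is significant at the 0.15 significance level". The next paragraph of SAP 6.2.2 asks for a Test/Control odds ratio with an unadjusted 95% interval and a simultaneous 99% interval. It does not say whether this is one overall odds ratio or five by visit.

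SAP 5.2.2 compares acuity, wear time and eyestrain between lenses at each time point with no lens-by-time condition. The 15% rules for eyestrain concern iris category only. The slit lamp analysis in SAP 6.2.2 carries no such condition either.

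**The concern.** If the interaction test does not reach 15%, the plan describes no formal comparison at any single visit, although the hypothesis is about each visit. The natural remaining result is one Test/Control odds ratio across weeks 1 to 12. A short-lived excess, for instance in the first week with a new lens, is the pattern that such an average dilutes most, and an interaction test spread over five visits has limited power at 50 to 60 subjects per arm.

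The direction matters because this is a safety endpoint with a hypothesis of no difference. A closed condition followed by a diluted, non-significant odds ratio could be taken as support at every visit when no visit was compared.

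**Working it through.** **1. The plan's own interval level.** Five visits with Bonferroni give 0.05/5 = 0.01, hence 99%. This reproduces the simultaneous interval in SAP 6.2.2. A single overall odds ratio would need no such adjustment, so the 99% level presupposes the five comparisons that the 15% condition can withhold.

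**2. The condition.** Two lenses and five visits give an interaction test with (2−1)×(5−1) = 4 degrees of freedom, judged at 0.15.

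**3. Dilution by averaging.** The documents give no symptom rate, effect or correlation, so the rates here are assumptions. Take an excess at week 1 only and average the five log odds ratios, so that the averaged odds ratio is the week-1 odds ratio to the power 1/5.

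| Control → Test, week 1 | Week-1 odds ratio | Averaged odds ratio | Mean excess over visits |
|---|---|---|---|
| 10% → 25% | (0.25×0.90)/(0.10×0.75) = 3.00 | 1.25 | 15/5 = 3 points |
| 20% → 40% | (0.40×0.80)/(0.20×0.60) = 2.67 | 1.22 | 20/5 = 4 points |
| 30% → 50% | (0.50×0.70)/(0.30×0.50) = 2.33 | 1.18 | 20/5 = 4 points |

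**4. Simulation, 60 per arm, 20% → 40% at week 1 only, both eyes agreeing.** There were 4,000 trials per setting, with saturated group-by-visit logits and empirical within-subject covariance. Latent correlations of 0.3 to 0.7 correspond to binary correlations of 0.16 to 0.45.

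| Latent correlation | Condition not met | Averaged odds ratio significant | Week 1 significant at 5%, no condition | Same, with condition | Loss |
|---|---|---|---|---|---|
| 0.3 | 36% | 13% | 67% | 53% | 14 points |
| 0.5 | 31% | 10% | 67% | 55% | 12 points |
| 0.7 | 20% | 10% | 69% | 60% | 9 points |

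A repeat run of this scenario gave 22–37% not met and 8–12% significant for the average. Week-1 detection fell from about 67% to 52–58% at the 5% level, and from about 41% to 36–38% at the adjusted 1% level.

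**5. Letting the two eyes differ.** Same rates and 60 per arm, with the subject taking 0.3 or 0.6 of the latent variance:
- The condition is not met in 25% or 16% of trials.
- Week-1 detection at 5% falls from 77% to 66%, or from 74% to 68%.
- Week-1 detection at 1% falls from 53% to 49%, or from 50% to 47%.

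**6. Planned completers, 50 per arm, eyes allowed to differ, all three scenarios of step 3.**
- The condition is not met in 21–41% of trials.
- The averaged odds ratio is significant in 9–12%.
- Removing the condition raises week-1 detection from 44–58% to 56–69% at 5%, a gain of about 8–16 points.
- At 1% it rises from 25–39% to 29–43%, a gain of about 3–5 points.
- In 5–11% of trials week 1 is significant at 5% while both the condition and the averaged test miss it.

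**7. The opposite pattern.** With the excess present at all five visits and 50 per arm (10% versus 25%, or 20% versus 40%), the condition stays unmet in about 82% of trials, but the averaged test detects the difference in 84–98%.

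**The case against.** A reader might infer that an early excess of symptoms would go unreported. The documents do not support that. Protocol 9.1 plans descriptive statistics at each time period for all safety variables, by lens type, and the SAP does not withdraw them. Protocol 8.1 lists ocular symptoms as a safety parameter and plans subject-level listings of all safety data. A split of 40% versus 20% at week 1 would be seen. What could be missing is its odds ratio, interval and test.

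Nor is it certain that visit-wise odds ratios are withheld. The odds-ratio paragraph in SAP 6.2.2 is itself unconditional, and its 99% interval suggests visit-wise output. The text "The assessments will be made at each follow-up visit" could also be read as a measurement schedule and not a promise of five tests. Both readings make the section ambiguous; neither reconciles it with its own 15% condition.

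The size depends on a pattern chosen to be unfavourable to an average. Even so, the 15% level is lenient and the condition is met more often than not. Sample size is the larger limit: at 50 per arm, with no condition at all, 31–44% of week-1 excesses of this size are missed at 5% and 57–71% at 1%.

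Reading a non-significant result as no difference is a separate weakness. It would remain after the change, at five visits instead of one.

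Finally, symptoms are a secondary endpoint, every hypothesis is labelled exploratory, and SAP 1.4 allows further analyses. That limits the priority but does not remove the conflict.

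**Conclusion.** The conflict stands: the symptom hypothesis, the multiplicity rule and the 99% interval all point to five visit-wise comparisons, while SAP 6.2.2 and Protocol 9.1 make them conditional. No other endpoint has a lens-by-time condition.

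The consequence is moderate and concerns the formal comparison only. For an assumed week-1-only excess of 20 points with 60 per arm and agreeing eyes, about 9–15 points of detection are lost at the unadjusted 5% level and about 3–5 at the adjusted 1% level. If the two eyes can differ, the loss at 5% is about 7–12 points. For a constant excess the averaged test largely makes up for the condition. These figures rest on assumed rates, timing and correlations, and on reading the fallback odds ratio as an average over visits, which the SAP does not state. The change is worth making because it resolves the contradiction at almost no cost, not because a confirmatory claim depends on it.

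**What to change.** In SAP 6.2.2, delete the 15% condition for ocular symptoms. State that Test/Control odds ratios are always reported at weeks 1, 2, 4, 8 and 12, each with an unadjusted 95% interval and the simultaneous 99% interval already specified. Add the overall odds ratio with its 95% interval and say how it is averaged over visits. Show the lens-by-time p-value as information only. Because the SAP supersedes Protocol section 9 where they differ, the SAP edit suffices; record that it replaces the matching condition in Protocol 9.1.

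The model already contains every term, so no new data or subjects are needed. The cost is five comparisons in place of one. If the unadjusted 95% intervals are read alone, the family-wise error could reach about 1 − 0.95^5 = 23% if the visits are taken as independent. The 99% intervals control this, so both sets should appear side by side.

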6.3. Adverse Events

Listings of all reported ocular and non-ocular AEs and SAEs will be reported. There will be separate summaries for adverse events, corneal inflammatory events (CIEs) and contact lens papillary conjunctivitis (CLPC).

6.4. Contact Lens Corrected Visual Acuity

A shift from the initial corrected lens visual acuity to the final corrected lens visual acuity will be presented across both eyes using counts and percentages for Safety test eyes. The aforementioned summary will also be broken out by visit. The count of the number of eyes that had a corrected lens visual acuity of 20/30 or better at the initial and final visits will be presented by completed and discontinued eyes. In addition, the count of the number of eyes with a visual acuity with lens within 1 and worse than 1 Snellen line of best corrected at the final visit will be reported for both completed and discontinued eyes. A detailed listing of eyes that worsened by 2 or more lines at final visit compared to baseline will be presented.

6.5. Unscheduled Lens Replacement

The number of unscheduled lens replacements and corresponding reasons will be tabulated by visit and overall across eyes for both completed and discontinued eyes.

6.6. Other Safety Parameters

Lens deposit, lens debris, Keratometry, and lens centration and movement will also be descriptively summarized.

7. REPORTING CONVENTIONS

P-values greater or equal than 0.0001 will be reported to 4 decimal places; p-values less than 0.0001 will be reported as “<0.0001”. All percentages will be reported to one decimal place. The mean and median will be reported to one decimal place greater than the original data. The standard deviation will be reported to two decimal places greater than the original data. Minimum and maximum will use the same number of decimal places as the original data.

8. QUALITY ASSURANCE MEASURES

8.1. Data Quality

Steps to be taken to ensure the accuracy and reliability of data include the selection of qualified investigators and appropriate study sites and review of protocol procedures with the principal investigator. The principle investigator, in turn, must ensure that all sub-investigators and study staff are familiar with the protocol and all study-specific procedures and have appropriate knowledge of the study article.

Guidelines for case report form completion will be provided and reviewed with study personnel before the start of the study. The case report forms will be reviewed for accuracy and completeness during monitoring visits and after transmission to data management. Any data discrepancies will be resolved with the investigator or designee, as appropriate.

Quality Assurance representatives from Johnson & Johnson Vision Care, Inc. may visit study sites to review data produced during the study and to assess compliance with applicable regulations pertaining to the conduct of clinical trials. The study sites will provide direct access to study-related source data/documents and reports for the purpose of monitoring and auditing by Johnson & Johnson Vision Care, Inc. and for inspection by local and regulatory authorities.

8.2. Statistical Programming

The statistical programming will follow analysis dataset specification as well as table shell specification. To ensure the validity of the analysis datasets as well as table and listing results, an independent program reviewer will be designated.

